3 STUDY DESIGN

3.1 Main study design

This study is a prospective, observational study to evaluate the safety of COVID-19 vaccine in 320 children and adolescents 5 - < 16 years-old receiving the vaccine per standard of care. Children and adolescents who have not received any previous COVID-19 vaccines will be enrolled with their first dose. Children and adolescents who have completed their primary vaccine series will enroll with their age-appropriate booster dose based on current FDA indications and CDC recommendations. With Day 1 serving as the day of vaccination, participants will be followed through Day 7 (total 7 days) after each dose of COVID-19 vaccine for symptoms of reactogenicity as described in **Section 5.1**. Participants will also be followed for 7 days after each vaccination for unsolicited adverse events, through day 181 for SAEs, and through day 181 for adverse events of special interest.

Demographic and medical history data will be collected and COVID-19 serostatus determined at baseline, and parent perceptions of COVID-19 vaccine will be assessed on Day 7 after each dose of vaccine. Participant perceptions will also be collected on Day 7 in adolescents aged ≥ 12 years.

3.2 Laboratory studies

3.2.1 Serologic studies

We will evaluate pre-serologic responses at three sites using an opt-in strategy. Prevaccination blood samples will be analyzed qualitatively for COVID-19 (SARS-CoV-2) antibody status (positive or negative) at Cincinnati Children's Hospital Medical Center in a CLIA-certified lab. Venous blood (approximately 5 mL of blood) will be collected from each participant in close proximity to the first vaccination (up to 3 days before or after vaccination). Venous blood will also be collected approximately 28 days after the second dose of vaccine received and stored for COVID-19 vaccine immunogenicity studies.

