7.2.1 Analysis Populations.....	27
7.2.2 Primary Objective	27
7.2.3 Secondary Objective	28
7.2.4 Exploratory Objective.....	29
7.2.5 Safety Monitoring Plan.....	29
7.3 Data Management Plan.....	29
7.3.1 Research Electronic Data Capture (REDCap).....	29
7.3.2 Role of the CDC Investigators in the Project.....	30
8 HUMAN SUBJECTS	30
8.1 Human Participants Involvement, Characteristics, and Design	30
8.2 Sources of Material.....	31
8.3 Potential Risks and Benefits.....	31

8.4 Adequacy of Protection	31
8.4.1 ClinicalTrials.gov Requirements	31
9.0 HUMAN SUBJECTS.....	31
9.1.1 Vulnerable Subjects.....	31
9.1.2 Vulnerable Subjects Research	32
REFERENCES	33

PROTOCOL SUMMARY

Title:	A Prospective Observational Study to Evaluate the Safety of COVID-19 Vaccination in Children and Adolescents
Phase:	Phase 4
Population:	Up to 320 male or female children and adolescents \geq 5 years to < 16 years
Clinical Sites:	Four: Duke University (Lead); Cincinnati Children's Hospital (Contributing); Kaiser Permanente (Contributing); Columbia University (Contributing)
Study Duration:	24 months
Participant Duration:	Approximately 7 months
Description of Study Procedures:	
This is a prospective, observational study to evaluate the safety of COVID-19 vaccination in children and adolescents receiving vaccine as part of standard of care. Children and adolescents who have not received any previous COVID-19 vaccines will be enrolled with their first dose. Children and adolescents who have completed their primary vaccine series will enroll with their age-appropriate booster dose based on current FDA indications and CDC recommendations.
 
Injection-site (local) and systemic reaction data and unsolicited adverse events will be assessed on vaccination day and daily during the 7 days following each COVID-19 vaccination dose using either identical web-based or paper memory aids, depending on study participant preference.
 
At 3 sites, serum samples will be collected for optional assessment of antibody titers to COVID-19. Each participant who opts in will have baseline (within 3 days of vaccination) serologies obtained. Serum samples will also be collected for immunogenicity assessments at 28 (+7) days after dose 2 or a booster dose.
 
All participants will be followed for 181 days after the last study dose 2 or a booster dose for serious adverse events (SAEs) and adverse events of special interest (AESI).

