EOM 1: Proportion of participants and legal guardians/parents with negative or positive perceptions of the vaccination experience based on participants responses to individual questions on the perceptions questionnaire

EOM 2: Assessment of primary outcome measures 1-6 in those with positive baseline COVID-19 serostatus versus those with a negative baseline serostatus

EOM 3: Proportion of participants with an adverse event of special interest through 6 months after dose 2 of COVID-19 vaccine or a booster dose

EOM 4: Proportion of participants with a serious adverse event through 6 months after dose 2 of COVID-19 vaccine or a booster dose

EOM 5a: The proportion of participants seropositive to SARS-CoV-2 variants tested prior to and following mRNA COVID-19 vaccine in a subset of children and adolescents

EOM 5b: The geometric mean ID₅₀ and ID₈₀ titers of neutralizing antibodies for each SARS-CoV-2 variant tested pre- and post-mRNA COVID-19 vaccine in a subset of child and adolescent participants.

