3.2.2 SARS-CoV-2 Antibody Assay

For children and adolescents at participating sites, optional blood draws will occur on Day 1 (before vaccination) and 28 (+7) days after dose 2 or a booster dose to be stored for serum COVID-19 neutralization assays. COVID-19 neutralizing antibody titers will be assessed for each variant tested. Participants will not receive individual COVID-19 antibody titer results; these are not routinely used in clinical practice.

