5 STUDY SCHEDULE, PROCEDURES, & EVALUATIONS

5.1 Schedule of Events

Children and adolescents meeting the proposed eligibility criteria (**Section 4.0**) will be recruited. Written informed consent will be obtained from study participants or their parent/guardian and assent from participants per local IRB requirements prior to conducting any study procedures. **Table 1** describes the schedule of study visits for children enrolling with their first COVID dose.

Table 1: Schedule of events: Primary Series (Dose 1 and 2)		Visit 1	Visit 1a	Visit 2	Visit 2a	Visit 3	Visit 4
Procedure	Type of contact	Clinic	Phone/Text /Email/Data Review a, b	Phone/Data Review c	Phone/Text/Email/Data Review a, b	Clinic/Phone d	Phone/Data Review
Time Relative to 1st COVID-19 Vaccine	1 (-3)	1-7 (+3)					
Time Relative to 2nd COVID-19 Vaccine			1 (+3)	1-7 (+3)	29 (+ 7)	181 (+/- 7)	
Informed consent & Medical Release of Information	X						
Review Eligibility Criteria	X						
Data Collection (Demographic information and Medical History)	X						
COVID-19 Vaccination History	X						
COVID-19 Disease History	X	X	X	X	X	X	
Concomitant Medications and Vaccines	X	X	X	X	X	X	
Standard of Care COVID-19 Vaccine	X		X				
Memory aid training + supplies (training on temperature)	X		X				
Blood draw ^e	X ^f				X		
Staff to review Memory aid form (REDCap or paper)		X	X	X			
Obtain solicited adverse events		X	X	X			
Obtain unsolicited adverse events		X	X	X			
Obtain serious adverse event information and AESIs		X	X	X	X	X	
Obtain parental and adolescent perceptions of COVID vaccine recommendations and receipt ^g		X		X			
Confirm date of next vaccine	X	X					
Confirm next study visit	X	X	X	X	X	X	

a. Memory aid (solicited local and systemic reactogenicity events) to be completed by LAR/participant on Days 1-7 after vaccination.

b. LAR/Participants completing paper diary only will be called 3 [+3] days after each dose of vaccine as a reminder and to prompt to bring paper diary to next visit

c. May be clinic visit if COVID vaccine is administered at research site

d. May be phone visit if not obtaining immunogenicity labs

e. Blood draws are optional and will be only performed at participating sites

f. Blood draw may be performed 3 days before or after vaccine

g. Adolescent perceptions of COVID-19 vaccine will be collected for adolescents (ages 12 - < 16 only)

Visit 1, Day of Vaccine or up to 3 Days Prior - Screening, Enrollment, and Vaccination (Clinic Visit)

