- Obtain parental permission by written informed consent and a release of medical record information, based on site IRB requirements
- Obtain assent from child, based on site IRB requirements
- Review and confirm study eligibility
- Obtain information on preferred method of contact for follow-up (telephone or email, or text reminder reminder)
- Obtain demographic data & COVID-19 vaccine history
- Obtain history of vaccines within 2 weeks of enrollment
- Obtain medical history, including COVID-19 disease history
- Obtain concomitant medication and vaccine use
- For children at participating sites, obtain optional blood sample within 3 days before or after vaccination for serologic analysis
- Dispense thermometer, ruler (in order to standardize measurements) and memory aid. Review instructions for use of thermometer, ruler, and memory aid completion. Preference will be to complete the memory aid electronically, with paper as a back-

up.

- Confirm anticipated date of COVID vaccine, if not already occurred
- Confirm date of next scheduled study visit

Visit 1a, Days 1-7 after dose 1 (Phone Visit)

- Subjects/parent/LAR will complete their memory aid via paper or electronic entry at approximately the same time each day for days 1-7, study staff will review subject-entered data within the database or by phone contact
- For participants using REDCap web-based system:
 - Study staff will send daily reminders to fill out the symptom diary
 - Record clinical data related to COVID diagnoses
 - Study staff will review REDCap system to confirm data capture and assess for any AE, AESIs, or SAEs on day 3 and 7 after vaccine
 - If any missing values, reported hives, or Grade 3 events occurred, the study staff will use phone contact to gather more information
 - The first parental and adolescent (if applicable) survey will be administered on day 7 after vaccine
 - Study staff will verify date of next COVID-19 vaccine and remind subjects to complete memory aid with next dose
- For participants using paper diary:
 - Study staff will call participants on day 3 after vaccine as a reminder to fill out the symptom diary
 - The first parent and adolescent (if applicable) survey will be administered on day 7
 - Study staff will call participants on day 7 (+ 3 days)
 - Record symptom diary
 - Record COVID-19 diagnoses
 - Record first parental and adolescent (if applicable) survey
 - Verify date of next COVID-19 vaccine and remind subjects to complete memory aid with next dose

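### The single baseline blood sample may be drawn up to 3 days after the dose, although the plan also calls it prevaccination and times it before vaccination, so post-dose results can enter the exploratory baseline values

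*Combined protocol and SAP*

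**What the plan says.** Section 3.2.1 describes the sample used for serostatus: "Prevaccination blood samples will be analyzed qualitatively for COVID-19 (SARS-CoV-2) antibody status (positive or negative". It then sets the collection time as "in close proximity to the first vaccination (up to 3 days before or after vaccination".

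Section 3.2.2, on the neutralization assay, states: "optional blood draws will occur on Day 1 (before vaccination) and 28 (+7) days after dose 2 or a booster dose".

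In Section 5.1, Table 1 footnote f (primary series) and Table 2 footnote e (booster) both read "Blood draw may be performed 3 days before or after vaccine". Both Visit 1 lists instruct staff to "obtain optional blood sample within 3 days before or after vaccination for serologic analysis". Yet both tables time Visit 1 at Day 1 with a 3-day allowance before and none after.

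The Protocol Summary says that each child who opts in "will have baseline (within 3 days of vaccination) serologies obtained", without saying on which side of the dose.

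EOM 2 (Section 2) compares the six primary outcome measures "in those with positive baseline COVID-19 serostatus versus those with a negative baseline serostatus". EOM 5a and 5b report seropositivity and geometric mean neutralizing titers before and after vaccination. Sections 7.2.3 and 7.2.4 leave the exploratory analysis to a separate comprehensive SAP. The document has no rule for a baseline sample drawn after the dose.

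**The concern.** A baseline value should not be open to influence from the exposure under study. Here the exposure is a Spike-based vaccine, and the ELISA in Section 6 measures IgG to Spike. Nothing in the document would separate an early vaccine response from antibody that was already there.

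Two consequences are possible:

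- **Measurement.** If antibody moves within 3 days, some truly negative children could be classed as positive for EOM 2, and the pre-vaccine titers in EOM 5b could be raised.
- **Completion of the draw.** EOM 2 compares reactions over Days 1-7. Where an optional draw falls after the dose, whether it takes place could depend on how the child is reacting. This route needs no antibody change.

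Sites could also work to different rules, depending on whether they follow Section 3.2.2 or the Section 5.1 footnotes. At stake is the interpretation of the serostatus comparison, which the Background presents as one of the gaps the study means to fill.

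**Working it through.** The plan gives no figure to reproduce here. The check is a comparison of the texts, followed by arithmetic on the windows and two conditional illustrations.

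**1. Draw times side by side**

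| Place | Permitted time relative to the dose |
|---|---|
| Protocol Summary | within 3 days, direction not given |
| Section 3.2.1 | -3 to +3 days, but labelled prevaccination |
| Section 3.2.2 | Day 1, before the dose |
| Table 1 footnote f; Table 2 footnote e | -3 to +3 days |
| Visit 1 lists, primary series and booster | -3 to +3 days |
| Visit 1 window, both tables | -3 to 0 days |

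**2. One sample or two?** Section 5.4.2 schedules specimens at Visits 1 and 3 (primary series) or Visits 1 and 2 (booster). Each table shows one baseline draw. Sections 3.2.1 and 3.2.2 therefore describe the same sample and cannot both hold.

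**3. Window.** From -3 to +3 is 3 + 1 + 3 = 7 calendar days, of which 3 follow the vaccination day. Vaccination is Day 1 (Section 3.1), so these are Days 2, 3 and 4. From -3 to 0 is 4 days, none after the vaccination day.

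**4. What has happened by the latest draw.** The diary starts on the evening of vaccination (Section 5.5). At a Day 4 draw, diary Days 1-3 of 7 are complete and Day 4 is in progress.

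**5. Subset size.** Section 5.4.2 excludes Columbia. From Section 4.3, 60 + 100 + 90 = 250 children at most, before opt-in. The number who opt in is not given.

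**6. Measurement effect on EOM 2, conditional.** Let π be true seroprevalence, f the share of draws made after the dose, and q the chance that such a draw turns a true negative positive. With an otherwise perfect assay and reclassification unrelated to reactions, the positive-minus-negative risk difference is multiplied by π / (π + (1 - π) f q). With f = 25% (assumed):

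| π | q = 0 | q = 2% | q = 10% |
|---|---|---|---|
| 6% | 1.00 | 0.06/0.0647 = 0.93 | 0.06/0.0835 = 0.72 |
| 50% | 1.00 | 0.5/0.5025 = 0.995 | 0.5/0.5125 = 0.98 |

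The 6% is the higher of two background figures in Section 1, from trials that excluded known prior infection. This study admits such children, so 6% is only an illustration. The 50%, f and q are assumptions.

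**7. Measurement effect on EOM 5b, conditional.** If titers in post-dose samples have risen r-fold, the pre-vaccine geometric mean is multiplied by r^f. The ratio of post to pre is then lower by 1 - 1/r^f.

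| f, r (assumed) | Pre-vaccine geometric mean | Post/pre ratio |
|---|---|---|
| 0.1, 1.2 | 1.018, up 2% | down 2% |
| 0.3, 1.5 | 1.129, up 13% | down 11% |
| 0.5, 2 | 1.414, up 41% | down 29% |

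If only a primed share p of children respond so early, the factor is r^(fp), which is smaller.

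**8. Effect of completion on EOM 2.** Let c1 and c0 be the chances of completing the draw with and without a reaction. Within each serostatus group the odds of a reaction are multiplied by c1/c0. If that ratio is the same in both groups, it cancels from the odds ratio, but the reported proportions and their difference still shift. Biasing the odds ratio requires c1/c0 to differ by serostatus, for example through known prior infection.

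**The case against.** The strongest reply is that this is mainly a wording slip. Section 3.2.2 is outnumbered by places that allow either side of the dose, 3 days may be too short for either assay to change, and only exploratory outcomes depend on the sample. The ELISA is a cut-off test run later in batches (Section 6), so knowledge of reactions should not alter its reading. The absence of an analysis rule here does not show that the comprehensive SAP lacks one. Most of this stands. It limits the size of the problem but does not remove the contradiction, because Section 3.2.1 conflicts with its own label and the footnotes conflict with the Visit 1 window.

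Three stronger readings are tempting:

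- A reader might infer that families choose serology after seeing the reactions. The documents do not show this. Section 5.1 puts consent before any study procedure, and Section 3.2.3 ties opt-in to agreeing to future use of samples, which points to a choice at consent. Consent pages are not in the text available. What remains is narrower: a child who has opted in may not complete a late optional draw.
- A reader might infer a demonstrated bias in EOM 2. Step 8 shows that dependence on reactions alone leaves the odds ratio intact, and no passage suggests joint dependence on serostatus.
- A reader might take 13% or 41% as lost fold rise. Those are inflations of the pre-vaccine geometric mean under assumed inputs; the matching falls are 11% and 29%. Fold rise is not a listed outcome, and the post-vaccine mean is unaffected.

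**Conclusion.** The contradiction holds. Followed as written, the plan can place post-exposure samples into baseline serostatus (EOM 2) and into the pre-vaccine values (EOM 5a and 5b), and no rule in this document deals with them. Completion of a late optional draw could also depend on reactions already recorded.

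The point is limited. No primary or secondary outcome is touched. The share of post-dose draws and any 3-day change in Spike IgG or neutralizing titer are not stated, so the bias cannot be sized and may be nil. The illustrations, with a multiplier on the EOM 2 risk difference from 1.00 down to 0.72 and a pre-vaccine geometric mean raised by 2% to 41%, rest wholly on assumed inputs and are not estimates for this study. The case for acting is that the remedy is cheap and the ambiguity can still be settled in the SAP.

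**What to change.** - **Protocol text.** Reconcile the Protocol Summary, Sections 3.2.1 and 3.2.2, Table 1 footnote f, Table 2 footnote e, both Visit 1 lists and the Visit 1 window on one draw time.
- **Data.** Record the draw time, or a before/after-dose flag, for every baseline sample. Sections 5.3 and 5.4 provide for the vaccination date and time, but Section 7.3.1 mentions only a sample collection date. Draws on later days can therefore be identified, but Day 1 draws cannot be placed before or after the injection.
- **SAP.** Define baseline for EOM 2, 5a and 5b as a sample drawn before the dose. State how many samples were drawn after it, and report results with and without them.

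The cost is a handful of wording changes, one data field and a short SAP definition. The only real downside is that children with only a post-dose sample leave the pre-dose analysis, from a subset of at most 250 before opt-in. The loss grows with the share of late draws, which the documents do not give. Those samples are still reported in the second analysis.

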3.2.2 SARS-CoV-2 Antibody Assay

For children and adolescents at participating sites, optional blood draws will occur on Day 1 (before vaccination) and 28 (+7) days after dose 2 or a booster dose to be stored for serum COVID-19 neutralization assays. COVID-19 neutralizing antibody titers will be assessed for each variant tested. Participants will not receive individual COVID-19 antibody titer results; these are not routinely used in clinical practice.

3.2.3 Future studies

In addition to the specified analyses described thus far, there might be other tests or assays that have yet to be identified that might be important for interpreting our study findings or of relevance to pediatric health outcomes. Additional laboratory assays may test for antibodies against other bacteria or viruses, markers of inflammation, or used in research on the health of children and adolescents. Specimens banked for use in other studies will be linked to information (including identifying information) that participants provided to the study. Participants in the opt-in serology analyses must agree to potential future use of samples in order to be in the study. Because it is unknown if future testing will be of any utility, results of future testing will not be provided.

4 STUDY ENROLLMENT AND WITHDRAWAL

Subject Inclusion and Exclusion Criteria will be reviewed at Visit 1 to assess eligibility for study participation.

4.1 Subject Inclusion Criteria

Subjects who meet all of the following criteria will be eligible to participate in this observational study.

1. Children \geq 5 years to < 16 years
2. Receiving first dose or a booster dose of a U.S. authorized or approved and recommended COVID-19 vaccine per standard of care.
3. Parent/legal authorized representative (LAR) willing to provide written informed consent per local IRB requirements
4. Participant willing to provide assent per local IRB requirements
5. Intention of being available for entire study period and complete all relevant study procedures, including follow-up phone calls
6. English or Spanish literate.

4.2 Subject Exclusion Criteria

Subjects who meet any of the following criteria will not be eligible to participate in this study:

1. Current or planned participation in any clinical trial with an investigational product during the study period.*
*Per protocol, co-enrollment in observational or behavioral intervention studies are permitted at any time. An investigational product may be permitted for therapy of an illness condition that occurs during the study period (e.g. COVID-19 illness)
2. Any condition, which, in the opinion of the investigators, may pose a health risk to the subject or interfere with the evaluation of the study objectives.
3. Anyone who is a relative of any research study personnel or is an employee supervised by study staff

4.3 Recruitment

The 320 participants in this study will be male or female children receiving COVID-19 vaccine per standard of care. Approximately 60 participants will be enrolled at Duke, 100 will be enrolled at Cincinnati, 70 will be enrolled at Columbia, and 90 will be enrolled at Kaiser Permanente.

Participants will be recruited from pediatric clinics and COVID-19 vaccination clinics affiliated with these sites. Medical records will be reviewed to identify, contact, and offer

study enrollment to potentially eligible children and adolescents. IRB-approved informational flyers/advertisements will be used to recruit children and adolescents receiving vaccination through public COVID-19 vaccination sites or clinics (primary care, or other clinic administering vaccine). Potential participants will be screened for eligibility and consented for study participation (if eligible) in-person (during routine care) or virtually (telephone or telehealth visit). Medical history, including vaccine history and COVID-19 disease history, will be obtained via participant and parent self-report with verification by chart review whenever feasible (including medical records, immunization registry records, and pharmacy records).

